- 309 • PMD with stimulus size V in the best eye qualifying for study entry
- 310 • Papilledema grade (Photographic Reading Center and site investigator ratings)
- 311 • OCT measures of:
 - 312 ♦ Retinal nerve fiber layer thickness
 - 313 ♦ Retinal ganglion cell layer thickness
 - 314 ♦ Peripapillary retinal pigment epithelial (RPE)/Bruch's membrane deformation
- 315 • CSF pressure
- 316 • Visual acuity
- 317 • Quality of life (QoL) measures (NEI-VFQ-25 + 10-item neuro-ophthalmic supplement
 318 and the SF-36)
- 319 • Headache disability (HIT-6 Inventory)
- 320 • Headache severity

321 Other efficacy outcome variables, determined at Month 6, include treatment failure, surgical
 322 failure, presence of headache, presence of transient visual obscurations, and visual field
 323 examination ratings (improved, no change, worse) by the Visual Field Reading Center.

324 With the exception of CSF pressure, these outcome variables will also be examined at Months
 325 12, 24 and 36.

326 Of special interest and a very important outcome is the time from randomization to treatment
 327 failure. Subjects will be followed for up to 3 years and the number of surgical failures and
 328 treatment failures will be analyzed. While a therapy may have a beneficial outcome at 6 months,
 329 it may not have a good outcome 1-3 years later; therefore, this is an important analysis.

330 Measures of safety include the following:

- 331 • Adverse events
- 332 • Serious adverse events
- 333 • Procedure complications and transient malfunctions of surgical procedures
- 334 • Blood pressure
- 335 • Laboratory test results (CBC with platelet count, electrolytes, potassium, bicarbonate, and
- 336 liver function tests)

337 **1.4.3 Other Outcomes**

- 338 • Anthropometric measures (weight, waist circumference)

339 **1.5 Potential Risks and Benefits of the Study Interventions**

340 **1.5.1 Known Potential Risks**

341 **1.5.1.1 Visual Loss**

342 The primary risk of IIH is visual loss associated with papilledema. Subjects reaching treatment
343 failure criteria will remain in the study but will be managed by the site investigators.

344 **1.5.1.2 Acetazolamide**

345 Acetazolamide frequently causes paresthesias, altered taste sensation, asymptomatic metabolic
346 acidosis (low serum bicarbonate), and fatigue. There is a small risk of kidney stones, and, very
347 rarely, renal failure from acute tubular necrosis, liver enzyme changes, elevation of serum

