7.1.2 Reporting Adverse Events

1188 Symptoms and signs, including visual symptoms and headaches, that are considered to be due to
1189 IIIH will be captured on a visit/phone case report form and are not considered to be adverse
1190 events unless SAE criteria are met.

1191 Certain adverse events that are known side effects of acetazolamide and furosemide will be
1192 captured on a visit/phone case report form (including paresthesia, dizziness, nausea, vomiting,
1193 diarrhea, loss of appetite, acid reflux, skin rash, dyspnea, hypercapnia, depression, anxiety,
1194 tinnitus, fatigue) for all subjects, regardless of whether taking study medication. A separate
1195 Adverse Event Form is only completed for these specific events if SAE criteria are met or the
1196 event was severe enough that it resulted in discontinuation of study drug.

1197 Expected symptoms post-surgery will be captured on a visit/phone case report form. A separate
1198 Adverse Event Form is only completed for these specific events if SAE criteria are met or if the
1199 onset date is outside the expected duration of occurrence post-surgery, regardless of intensity.

1200 Laboratory results of interest will be recorded on a laboratory data case report form. A separate
1201 Adverse Event Form is only completed for laboratory abnormalities that are considered clinically
1202 significant by the investigator.

1203 During the first 6 months, all other events (not described above) meeting the definition of
1204 adverse event will be reported on an Adverse Event Form. After the first 6 months, only those
1205 events meeting SAE criteria will be reported on an Adverse Event Form.

1206 **7.1.3 Relationship of Adverse Event to Study**

1207 The study investigator will assess the relationship of any adverse event reported on an Adverse
1208 Event Form to be related or unrelated to a study intervention or procedure by determining if there
1209 is a reasonable possibility that the adverse event may have been caused by the intervention or
1210 procedure.

1211 To ensure consistency of adverse event causality assessments, investigators should apply the
1212 following general guideline when determining whether an adverse event is related:

1213 Yes

1214 There is a plausible temporal relationship between the onset of the adverse event and the study
1215 intervention/procedure, and the adverse event cannot be readily explained by the subject's

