1250 will be updated and recorded as “resolved” with the date of death recorded as the stop
1251 date.
- 1252 • FATAL: A fatal outcome is defined as the SAE that resulted in death. Only the event
1253 that was the cause of death should be reported as fatal. AEs/SAEs that were ongoing at
1254 the time of death; however, were not the cause of death, will be recorded as “resolved” at
1255 the time of death.
- 1256 • UNKNOWN: An unknown outcome is defined as an inability to access the subject or the
1257 subject’s records to determine the outcome (for example, a subject that was lost to
1258 follow-up).

1259 All clinically significant abnormalities of clinical laboratory measurements or adverse events
1260 occurring during the study and continuing at study termination should be followed by the
1261 subject’s physician and evaluated with additional tests (if necessary) until diagnosis of the
1262 underlying cause, or resolution. Follow-up information should be recorded on source
1263 documents.

1264 If any reported adverse events are present when a subject completes the study, or if a subject is
1265 withdrawn from the study due to an adverse event, the subject will be contacted for re-evaluation
1266 within 2 weeks. If the adverse event has not resolved, additional follow-up will be performed as
1267 appropriate. Every effort should be made by the Investigator or delegate to contact the subject
1268 until the adverse event has resolved or stabilized.

1269 **7.2 Pregnancy Reporting**

1270 If pregnancy occurs during the 6-month RCT, study drug will be discontinued. The occurrence of
1271 pregnancy will be reported on an AE Form.

1272 **7.3 Timing of Event Reporting**

1273 Serious, unexpected treatment-related adverse events must be reported to the Coordinating
1274 Center within 24 hours via completion of the online serious adverse event form.

1275 Other reportable adverse events as defined in section 7.1.2 will be reported within 3 days of the
1276 investigator becoming aware of the event by completion of an electronic case report form.

1277 The Coordinating Center will notify all participating investigators of any adverse event that is
1278 serious, related, and unexpected. Notification will be made within 10 working days after the
1279 Coordinating Center becomes aware of the event.

1280 Each principal investigator is responsible for reporting serious study-related adverse events and

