 1478 eyes will have this information summarized by eye as well as by treatment group and visit.
 1479 Change in weight will be used as a summary of compliance with diet.

1480 **9.6 Analysis of Safety and Tolerability Outcomes**

1481 **9.6.1 Adverse Events**

1482 All reportable adverse events will be tabulated by treatment group in a listing of each reported
 1483 Medical Dictionary for Regulatory Activities (MedDRA) term and summarized over each
 1484 MedDRA System Organ Class. Details will be provided in a listing of each event.

1485 In addition, the following will be tabulated by treatment group. When applicable, events will be
 1486 tabulated by eye within person:

- 1487 • Number of adverse events
- 1488 • Number of subjects with at least one event
- 1489 • Number of serious adverse events
- 1490 • Number of subjects with at least one serious adverse event
- 1491 • Number of hospitalizations and reasons for the hospitalization

- 1492 • Number of adverse events thought by investigator to be related to study drug
- 1493 • Number of subjects who stopped the intervention in response to an adverse event

1494 For binary variables, Fisher exact tests will be used to compare treatment groups. For counts,
1495 groups will be compared using Poisson regression.

1496 For each adverse event, the treatment groups will be compared in a pair-wise fashion regarding
1497 the occurrence of at least one event using Fisher's exact tests; numbers of individual events will
1498 also be described. The comparisons will be repeated excluding all mild symptoms. Similar
1499 analyses will be performed after grouping adverse events by body system using Medical
1500 Dictionary for Regulatory Activities (MedDRA) coding. All subjects will be included in these
1501 analyses.

1502 **9.6.2 Tolerability Outcomes**

1503 Tolerability will be primarily measured by ability to complete 6 months of follow-up on the
1504 originally assigned treatment. A complete accounting of subject disposition will be summarized
1505 by treatment group, including a tabulation of subject withdrawals, dosage reductions/
1506 discontinuations of study medication due to adverse events (with reasons for each), receipt of
1507 surgery other than that randomly assigned, and surgical failures.

1508 **9.6.3 Laboratory Test Results and Vital Signs**

1509 Continuous measures of safety such as laboratory test results (e.g., CBC with platelet count,

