416 Assessment for and implementation of adjustment for baseline covariates will follow methods
417 described in *Section 3.2.3*.

419 **3.3.4 Investigation of Treatment by Covariate Interactions**

420 Investigation of interaction between treatment group and selected baseline covariates will follow
421 methods described in *Section 3.2.4*.

422

423 **3.3.5 Verification of Model Assumptions**

424 Methods described in *Section 3.2.5* will be used to check underlying assumptions of the
425 statistical model for each outcome.

426

427 **3.3.6 Treatment of Missing Data**

428 Methods described in *Section 3.2.6* will be used to impute missing data at Month 6 for
429 continuous outcomes.

430

431 Missing values of Month 6 visual field examination status will not be imputed.

432

433 **3.4 Compliance Outcomes**

434 Data concerning compliance with acetazolamide (pill counts, serum bicarbonate levels) and
435 surgical therapy will be summarized by treatment group and visit. Subjects with two eligible
436 eyes will have this information summarized by eye as well as by treatment group and visit.

437

438 **3.5 Analysis of Safety and Tolerability Outcomes**

439 **3.5.1 Adverse Events**

440 All reportable adverse events will be tabulated by treatment group in a listing of each reported
441 Medical Dictionary for Regulatory Activities (MedDRA) term and summarized over each
442 MedDRA System Organ Class. Details will be provided in a listing of each event.

443 In addition, the following will be tabulated by treatment group. When applicable, events will be
444 tabulated by eye within person:

- 445 • Number of adverse events per subject
- 446 • Number of subjects with at least one event
- 447 • Number of subjects with at least one event per person-month (person-month based on
448 subject duration in the study)
- 449 • Number of serious adverse events per subject
- 450 • Number of subjects with at least one serious adverse event
- 451 • Number of hospitalizations and reasons for the hospitalization (overall and per subject,
452 separately)
- 453 • Number of adverse events thought by investigator to be related to study drug and
454 frequency of each type of such event
- 455 • Number of subjects who stopped the intervention in response to an adverse event

456 For binary variables (occurrence of at least one event, occurrence of at least one serious adverse
457 event, occurrence of at least one hospitalization, occurrence of at least one adverse event related

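### As written, the SAP's between-arm adverse event comparison leaves out the drug side effects and expected post-surgical symptoms kept on the visit/phone forms, and the SAP does not carry over the protocol's primary tolerability measure

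*SAP*

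**What the plan says.** **What is collected, and where.** Protocol 7.1.2 states that known side effects of acetazolamide and furosemide are "captured on a visit/phone case report form (including paresthesia, dizziness, nausea, vomiting" and others, ending with "tinnitus, fatigue) for all subjects, regardless of whether taking study medication. A separate" form is needed only in limited cases: "Adverse Event Form is only completed for these specific events if SAE criteria are met or the" event was severe enough to lead to discontinuation of study drug. Fourteen effects are named. For surgery, "Expected symptoms post-surgery will be captured on a visit/phone case report form. A separate" form is again the exception, used if the symptom is serious or begins outside the period in which it is expected, whatever its intensity. In the first 6 months, other events meeting the adverse event definition go on an Adverse Event Form. Clinically significant laboratory abnormalities go there too.

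**What is analysed.** SAP 3.5.1 opens with "All reportable adverse events will be tabulated by treatment group in a listing of each reported" MedDRA term. Tabulations, Fisher's exact tests and Poisson regression of counts follow. The SAP does not define 'reportable' and does not mention the visit/phone forms. Protocol 9.6.1 opens with the same sentence.

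**Tolerability.** Protocol 9.6.2 says "Tolerability will be primarily measured by ability to complete 6 months of follow-up on the" treatment originally assigned. It also asks for a by-group account of disposition, including dose reductions and discontinuations for adverse events, with reasons. SAP 3.5 has tolerability in its heading but contains only 3.5.1 (adverse events) and 3.5.2 (laboratory tests and vital signs).

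**The concern.** The three arms carry different kinds of harm, so the safety comparison is only as good as the set of events it counts. The protocol calls some of the drug effects common: "Acetazolamide frequently causes paresthesias, altered taste sensation, asymptomatic metabolic" acidosis and fatigue (Protocol 1.5.1.2). Paresthesia and fatigue are both on the list kept on the visit/phone form.

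All arms start acetazolamide, but Protocol 4.1.4 and 4.3 have VPS subjects taper from the day of surgery, while the other two arms titrate upward as tolerated. Drug side effects are therefore likely to differ by arm. A count that drops the non-serious ones tends to flatter the arms with more drug exposure. A count that drops expected post-surgical symptoms tends to flatter the surgical arms. The net direction is unknown, but the number of adverse events per subject would not describe the harm that subjects had, and it is one of the quantities SAP 3.5.1 compares between groups.

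**Working it through.** This is mainly a comparison of texts. The plan states no figure to reproduce.

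**Step 1. What 'reportable' means.** Protocol 7.1.1 refers to 7.1.2 for which adverse events require reporting. Protocol 7.3 does the same: "Other reportable adverse events as defined in section 7.1.2 will be reported within 3 days of the" investigator learning of them. In 7.1.2, reporting means completing an Adverse Event Form, and the visit/phone-form items are set apart from it. Protocol 7.5 also lists Adverse Event Form events and solicited visit/phone-form events as separate categories. The natural reading of 'reportable' is therefore an event that needs an Adverse Event Form.

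**Step 2. Follow each type of event into the SAP.**

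| Event | Adverse Event Form? | Counted in SAP 3.5.1? | Named elsewhere in the SAP? |
|---|---|---|---|
| Listed drug effect, serious | Yes | Yes | – |
| Listed drug effect, drug stopped | Yes | Yes | Stopping for an adverse event is also tabulated and tested |
| Listed drug effect, dose reduced only | No | No | Dosage by visit (3.8), without reasons |
| Listed drug effect, no dose change | No | No | No |
| Expected post-surgical symptom, serious or outside expected period | Yes | Yes | – |
| Expected post-surgical symptom, otherwise | No | No | No |
| Surgical complications, reoperations, shunt revisions | Depends on event | Depends on event | Yes (3.8) |
| Laboratory abnormality | If clinically significant | If on the form | Yes, pair-wise tests (3.5.2) |

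Rows marked 'No' assume that the event is not serious. Headache has its own by-visit table in 3.8; no other solicited symptom does.

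The dose-reduction row is not a corner case. Protocol 4.1.1.4 allows stepwise lowering for intolerance, down to 125 mg. Protocol 1.3.2.1 reports that 40% of subjects in the earlier trial could tolerate 4 g per day. The remaining 100% − 40% = 60% are not broken down by reason, so this does not give a side-effect rate, but it shows that reaching less than the full dose was common.

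**Step 3. Protocol 9.6.2 against the SAP.**

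| Component of 9.6.2 | In the SAP? |
|---|---|
| Completion of 6 months on originally assigned treatment (primary measure) | No |
| Withdrawals | Yes, flow chart with reasons (3.8) |
| Discontinuation for an adverse event | Yes, tabulated and tested (3.5.1) |
| Dose reductions for adverse events, with reasons | No; only dosage by visit (3.8) |
| Surgery other than assigned | Yes (3.8) |
| Surgical failures | Yes, as surgical malfunctions (3.8) |

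**Step 4. Can the omission be sized?** No. The documents give no side-effect or symptom rates by arm. A narrower question is whether a by-arm comparison of one solicited item could be informative. Purely as an assumption, take paresthesia in 40% or 50% of medical subjects and 15% or 20% of VPS subjects, with 60 per arm. Power is the sum of Bin(x; 60, p₁)·Bin(y; 60, p₂) over all (x, y) at which the two-sided Fisher p-value is at most 0.05/3 = 0.0167:

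| Medical | VPS | Power |
|---|---|---|
| 40% | 20% | 43% |
| 40% | 15% | 71% |
| 50% | 20% | 83% |
| 50% | 15% | 95% |

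The range is 43% to 95%. The 1.7% level is borrowed from the efficacy analysis; SAP 3.5.1 sets no level for its safety tests. These figures show that the comparison could be informative. They do not measure how much harm goes uncounted.

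**The case against.** The strongest reply is that exclusion is inferred rather than stated. The SAP leaves 'reportable' undefined, and Protocol 7.5 has the Medical Monitor assess each reviewed event, solicited ones included, for intensity, relationship and MedDRA class. That could support a wider reading in which solicited events are tabulated too. This stands as a caution. It does not remove the problem, because the two readings give very different counts and the choice should not be left until the data are seen.

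A reader might also infer that the arms are compared without their most frequent harms. The documents do not support that. Of the acetazolamide effects called frequent, metabolic acidosis falls under the laboratory comparisons, and altered taste is not among the 14 named visit/phone-form items. Hypokalemia, a common furosemide effect, is also a laboratory finding, and blood pressure is summarised. Surgical complications, reoperations and shunt revisions are tabulated. Nothing says that expected post-surgical symptoms are the most frequent surgical harms.

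Nor is tolerability absent from the SAP, since most 9.6.2 components appear there. Protocol 9.6.2 also remains in version 4.0, which is later than the SAP, so the completion measure is still pre-specified in the protocol. It asks for a summary by group, not a test.

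Finally, pair-wise tests of 14 items across three arms would add 14 × 3 = 42 tests, and expected symptoms of an orbital and a cranial-abdominal procedure are not like for like. Both points stand and shape the fix.

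**Conclusion.** The concern holds in a limited form. On the natural reading of 'reportable', the between-arm adverse event comparison omits listed drug effects that are neither serious nor a cause of stopping the drug, including those that force a dose reduction. It also omits post-surgical symptoms that are not serious and fall within their expected period. No SAP table picks up either group. Because drug exposure differs by assigned arm, the undercount is likely to differ by arm as well. Separately, the SAP lacks the primary tolerability measure of Protocol 9.6.2 and dose reductions for adverse events with reasons.

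The conclusion rests on reading 'reportable' through Protocol 7.1.1, 7.1.2 and 7.3. If the wider reading was intended, the defect is an undefined term rather than an omission, and part of the same fix settles it. The size and net direction of any distortion cannot be determined from the documents. The primary efficacy analysis is not affected. The change should be made before outcome data are examined.

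**What to change.** In SAP 3.5.1:

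1. State that 'reportable' means events recorded on an Adverse Event Form.
2. Add by-arm tables through Month 6 for each solicited drug side effect: the number of subjects ever reporting it after baseline, and the proportion of visits at which it was present. Give between-arm differences with confidence intervals, or Fisher's exact tests, labelled exploratory.
3. Tabulate expected post-surgical symptoms descriptively within ONSF and within VPS, without testing one against the other.
4. Keep these tables separate from Adverse Event Form counts, so that one persistent symptom is not counted again at each visit.

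In SAP 3.5, under a tolerability subsection:

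5. Add the 9.6.2 completion measure by arm, with a rule for what counts as remaining on the assigned treatment in each arm.
6. Add dose reductions due to adverse events by arm, with reasons.

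Protocol 9.6.1 should be given the same definition of 'reportable'.

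The cost is SAP wording and a few tables. The side-effect and symptom data are already collected under Protocol 7.1.2. The downside is exploratory multiplicity if tests are used, which labelling or reporting intervals alone would handle.

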
Sample Size
	
180 subjects entering randomized trial
 
 90% power to detect a difference in mean change of visual field between groups assuming a true population difference between any 2 of 3 groups = 4.5dB with a two-tailed Bonferroni-adjusted significance level of 1.7%, assuming no more than 10% of subjects withdrawing.

PARTICIPANT AREA	DESCRIPTION
Treatment Groups	Random assignment (1:1:1) to (1) medical therapy, (2) medical therapy plus ONSF, or (3) medical therapy plus VPS.
Subject Duration	~7 months- 3 years

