- 921 **Chapter 5: Study Visits and Procedures**
- 922 **5.1 Randomized Trial**
- 923 **5.1.1 Study Visits and Phone Contacts**
- 924 During the randomized trial, follow-up visits for all three groups will occur at weeks 4, 8 16, and
925 26 (± 7 days) timed from the day of randomization.
- 926 Post-operative visits may also be performed by the surgeon according to the surgeon's usual
927 routine.
- 928 Additional office visits may occur as needed.
- 929 Phone contacts will occur at 12 and 20 weeks (± 7 days).
- 930 **5.1.2 Safety Visits**
- 931 Safety visits will occur in addition to study visits, with the timing dependent on the treatment
932 group. The medical therapy only group generally will have visits 7 days and 14 days (± 4 days)
933 following randomization whereas the surgery groups generally will have visits 7 days and 14
934 days (± 4 days) following each surgical procedure. Visit schedules can be modified at
935 investigator discretion based on the participant's course and the 14-day visit could be skipped if
936 there is substantial improvement in papilledema after 7 days. Additional visits can be scheduled
937 as indicated. Reoperations at any time also will have a similar safety visit schedule.
- 938 **5.1.3 Study Visit Procedures**
- 939 The following procedures will be performed for all subjects at each study visit, unless otherwise
940 specified:
- 941 • Medical/IIH history update
 - 942 • Adverse Events
 - 943 • Concomitant Medications
 - 944 • Vital signs, including weight; (waist circumference at 26 Week only)
 - 945 • Clinical Laboratories
 - 946 • Refraction
 - 947 • Visual Acuity
 - 948 • Ocular Examination
 - 949 • Metabolic Panel (16 and 26 Week only)
 - 950 • CBC (16 and 26 Week only)
 - 951 • Humphrey visual field testing with 24-2 full-threshold program using size V stimulus
 - 952 ➤ at 26 Week, two visual field examinations

953 ➤ At other study visits, one visual field examination will be done, but the VFRC may
954 request the visual field examination be repeated

- 955 • Fundus Photographs
- 956 • OCT* (optic nerve head and macula)
- 957 • Dispense/prescribe acetazolamide and, if needed, furosemide
- 958 • Drug Compliance/Accountability
- 959 • Dietary counseling
- 960 • QoL questionnaires (26 Week only) – at study site or online
- 961 • HIT-6 questionnaire (26 Week only) – at study site or online
- 962 • Lumbar puncture for CSF opening pressure measurement (26 Week; voluntary)

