963 *The 26 Week OCT must be done *before* the lumbar puncture.

964 **5.1.4 Phone Contact Procedures**

965 The Site Coordinator will contact the subject by telephone to review adverse events.

- 966 • Medical/IIH History update
- 967 • Adverse Events
- 968 • Review of Concomitant Medications
- 969 • Review of Drug Compliance

970 Additional phone contacts, texts, and emails may be performed as needed.

971 **5.1.5 Safety Visit Procedures**

972 The following procedures will be performed for all subjects at each safety visit:

- 973 • Adverse Events
- 974 • Concomitant Medications
- 975 • Vital signs, including weight
- 976 • Refraction
- 977 • Visual Acuity
- 978 • Ocular Examination
- 979 • Humphrey Visual Field testing with 24-2 full-threshold program using size V stimulus
- 980 • OCT (optic nerve head and macula)
- 981 • Fundus Photographs (only at week 2)
- 982 • Drug Compliance/Accountability

983 **5.2 Treatment Failure Identification Phase**

984 **5.2.1 Follow-up Visits**

985 Follow-up visits will occur at weeks 52 (12 months), 104 (2 years), and 156 (3 years) +4 weeks
986 as long as the study is ongoing.

987 **5.2.2 Study Visit Procedures**

988 Procedures at these visits will include the following:

- 989 • Medical/IIH history update (includes all new treatments and adjustments of dosages)
- 990 • Adverse Events
- 991 • Concomitant Medications
- 992 • Vital signs, including weight
- 993 • Refraction
- 994 • Visual Acuity
- 995 • Ocular Examination
- 996 • Humphrey Visual Field testing with 24-2 full-threshold program using size V stimulus
- 997 • Fundus Photographs
- 998 • OCT (optic nerve head and macula)
- 999 • Drug Compliance
- 1000 • QoL questionnaires – at study site or online
- 1001 • HIT-6 questionnaire – at study site or online

1002 If subject wants to discontinue birth control after the 6-month RCT, this should be discussed with
1003 the Site Investigator.

1004 **5.2.3 Phone Contact Procedures**

1005 A phone, text or email contact will occur at 39 weeks by site staff. Subsequent contacts (every 3
1006 months, starting at month 15 through month 33) will be by Coordinating Center staff for a
1007 structured interview to determine if IIH symptoms have worsened. If the caller has concerns
1008 about the subject, the site investigator will be notified and will be responsible for contacting the
1009 subject.

1010 **5.3 Unscheduled Visits**

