458 to treatment, occurrence of stopping the intervention in response to adverse event), Fisher exact
459 tests will be used to compare treatment groups. For counts (number of adverse events per
460 subject, number of serious adverse events per subject, number of hospitalizations per subject),
461 groups will be compared using Poisson regression with inclusion of the logarithm of study
462 follow-up duration for the participant as an offset term; a negative binomial model will be
463 considered if overdispersion is present, and a zero-inflated negative binomial model will be used
464 if there appear to be excessive zero counts.

465 For each adverse event, the treatment groups will be compared in a pair-wise fashion regarding
466 the occurrence of at least one event using Fisher's exact tests; numbers of individual events will
467 also be described. The comparisons will be repeated excluding all mild symptoms. Similar
468 analyses will be performed after grouping adverse events by body system using Medical
469 Dictionary for Regulatory Activities (MedDRA) coding. All subjects will be included in these
470 analyses.

471

472 **3.5.2 Laboratory Test Results and Vital Signs**

473 Continuous measures of safety such as laboratory test results (CBC with platelet count,
474 electrolytes, potassium, bicarbonate, and liver function tests) and vital signs and anthropometric
475 measures (blood pressure, weight, and waist circumference) will be analyzed descriptively
476 through summary statistics and tabulations.

477 Proportions of subjects with particular laboratory test abnormalities will be compared between
478 the treatment groups in a pair-wise fashion using Fisher's exact tests.

479

480 **3.6 Analysis of Long-Term Follow-Up Data**

481 The following outcome will be examined in analysis of long-term follow-up data:

- 482 • Time from randomization to treatment failure

483

484 **3.6.1 Analysis Model**

485 Treatment group differences with respect to long-term outcomes will be assessed by fitting a Cox
486 proportional hazards regression model with treatment group as the factor of interest and baseline
487 PMD in the best eligible eye as a covariate. Due to the discrete time data, Efron approximation
488 will be used to deal with tied event times. The model will be used to determine Bonferroni-
489 adjusted 98.3% confidence intervals for the adjusted hazard ratios for the three pair-wise

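### The all-AE count model and the any-event person-month line take whole-study follow-up as exposure, although only SAEs go on the Adverse Event Form after Month 6.

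*SAP*

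**What the plan says.** SAP 3.5.1 specifies one count model for three outcomes: all adverse events per subject and, in its words, "subject, number of serious adverse events per subject, number of hospitalizations per subject". For all three, "groups will be compared using Poisson regression with inclusion of the logarithm of study" and then "follow-up duration for the participant as an offset term; a negative binomial model will be" considered if there is overdispersion.

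The same section lists a tabulation, "Number of subjects with at least one event per person-month (person-month based on" each subject's duration in the study).

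The Protocol Summary gives subject duration as about "7 months- 3 years". Protocol 5.2.1 runs the annual visits "as long as the study is ongoing", so follow-up after Month 6 depends on when a subject enrolled.

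Protocol 7.1.2 sets what is collected. Some solicited side effects, expected post-surgical symptoms and laboratory results have their own form rules. During the first 6 months every other event meeting the definition of an "adverse event will be reported on an Adverse Event Form. After the first 6 months, only those" meeting SAE criteria are reported there. Protocol 7.3 ties the term reportable to 7.1.2, and SAP 3.5.1 tabulates all reportable adverse events without naming a period.

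**The concern.** The numerator changes definition at Month 6 and the denominator does not. A non-serious AE outside the special form rules can be counted for about 6 months only, but the subject goes on adding exposure until the end of follow-up. The rate then depends partly on how long people happened to be followed. A reader shown an AE rate per person-month would take it for an incidence. If retention after Month 6 differed between arms, the arm followed for less time would appear to have the higher AE rate.

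**Working it through.** **No figure to reproduce.** The documents give no AE rate, exposure total or power for the AE comparisons. The mismatch can be read from the text; its size needs assumptions.

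**Single subject.** For a non-serious event type collected for 6 months only, the rate is understated by follow-up/6: 7/6 = 1.17 at 7 months, 2 at 12, 4 at 24 and 6 at 36.

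**Assumptions for the whole trial.**
- The 36-month accrual period is in SAP 3.7.2. Uniform accrual is also the SAP's working assumption there.
- Closure when the last subject reaches 7 months is my assumption, chosen to match the stated minimum duration.
- With enrolment time E uniform on 0 to 36, follow-up is F = min(36, 43 - E). Its mean is (7 x 36 + 29 x 21.5)/36 = 24.32 months.
- m is the number of AEs per subject in the first 6 months, assumed 1 to 5.
- s is the share of those AEs that are of a type still collected later at the same rate, assumed 0.1 to 0.3. I also tried 0.5, in case the special form rules in Protocol 7.1.2 keep more events in.

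**All-AE rate implied by the count model.** The rate over the first 6 months is m/6. As written, the expected count is m[1 + s(F - 6)/6] over exposure F. The understatement is 24.32/[6(1 - s) + 24.32s], and m cancels.
- s = 0.1: 24.32/7.83 = 3.11
- s = 0.3: 24.32/11.50 = 2.12
- s = 0.5: 24.32/15.16 = 1.60

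**Ratio between arms.** With the same follow-up distribution in each arm, the factor cancels and the ratio is unbiased. As an illustration, assume equal true rates and attrition after Month 6 of 5% a year in one arm and 15% in the other. Mean follow-up is then 23.44 and 21.75 months. The spurious ratio is {[6(1 - s) + 21.75s]/21.75} / {[6(1 - s) + 23.44s]/23.44}.
- s = 0: 1.078
- s = 0.1: 1.054
- s = 0.3: 1.029

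**Any-event person-month line.** The 6-month figure is (1 - exp(-m))/6. As written, the line is the mean of 1 - exp[-m - ms(F - 6)/6], divided by 24.32. Setting s = 1, so that every AE stays reportable, shows how much of the gap is due to the reporting rule.

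| m | s | 6-month figure / line as written | Same with s = 1 | Part due to the reporting rule |
|---|---|---|---|---|
| 1 | 0.1 | 3.53 | 2.70 | 1.31 |
| 1 | 0.3 | 3.07 | 2.70 | 1.13 |
| 5 | 0.1 | 4.03 | 4.03 | 1.00 |

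Most of the gap arises because a subject counts once while person-time runs on after the first event.

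**Test size.** This was simulated for a plain Poisson Wald test on one pair of arms at nominal 5%, with 20,000 runs per setting. There were 180 subjects in three strata, with permuted blocks of 3, 6 or 9 (the block size is not stated).
- No attrition, s = 0.1 to 0.3: 4.7-5.5%.
- 10% a year attrition after Month 6, same s: 5.0-7.5%.
- First-6-month events with 6-month exposure: 4.6-5.1%.

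**The case against.** **Perhaps all of SAP 3.5.1 was meant for the 6-month trial.** SAP 3.6 names only time to treatment failure as a long-term outcome, SAP 3.8 tabulates the 6-month trial separately, and study follow-up duration is never defined. Under that reading one common offset would be coherent. It cannot be excluded as the intention. But SAP 3.5.1 does not say so, its person-month line refers to duration in the study, and SAEs are collected throughout. The whole-study reading is the natural one, and the cutoff has to be written down either way.

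**A reader might infer that the reporting rule makes the person-month line three to four times too low.** The arithmetic does not support that. A 2.7- to 4.0-fold gap would remain if every AE stayed reportable. The rule alone adds a factor of about 1.1 to 1.3 at one AE per subject in 6 months, and almost nothing at five.

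**A reader might also infer that the AE comparison has an inflated error rate.** The Poisson figures above 5% hold only if the negative binomial option is not used. The mis-set offset itself creates overdispersion, which could trigger that option. In a smaller simulation (800 runs per setting, 10% a year attrition) the negative binomial rejected about 2-3%, so it was conservative. It corrects the variance, but the diluted rate remains.

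**Bias between arms is hypothetical.** Nothing in the documents predicts different retention, and the 5% and 15% figures are only an illustration. This objection stands.

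**Conclusion.** The mismatch is real and minor. As written, the all-AE rate from the count model is understated about 2.1- to 3.1-fold if 10-30% of first-6-month AEs are of a type still collected later, and 1.6-fold if 50% are. These figures rest on the assumed accrual and closure pattern (mean follow-up 24.3 months). The direction does not depend on those assumptions; the size does.

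The documents do not support a claim that the between-arm AE comparison is biased. That needs follow-up to differ by arm, and the illustrated attrition gap moves the ratio only to about 1.03-1.05, or 1.08 if the SAE share is negligible. The person-month line has the same mismatch, but most of its distance from the 6-month figure has another cause. SAE counts are unaffected, and so are hospitalizations, because inpatient hospitalization is itself an SAE criterion in Protocol 7.1.1. Raw per-subject counts and Fisher tests do not use the exposure term.

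**What to change.** In SAP 3.5.1:
- Restrict the all-AE count model and the person-month line to events with onset from randomization to a fixed study day, for example Day 182 (26 x 7, the target day of the Month 6 visit).
- Use min(follow-up, cutoff) as the exposure and its log as the offset.
- If the person-month line is to be read as an incidence rate, also end each subject's person-time at the first event.
- Keep full follow-up as exposure for SAE and hospitalization counts, so that later SAEs are still analysed there, and label the two periods in the tables.

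A small mismatch can remain if a site stops full AE reporting at the Month 6 visit. Protocol 5.1.1 sets that visit at week "26 (± 7 days) timed from the day of randomization", so the earliest in-window visit is Day 175 and the mismatch is at most 7/182 = 3.8%. SAP 3.2.1 accepts outcome testing from Day 168, which gives 14/182 = 7.7%.

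The cost is SAP wording and one derived exposure variable. No new data are needed.
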